4.2.8.5 Physical examination

Any new finding(s) or aggravated existing finding(s), judged as clinically significant by the Investigator, will be reported as an AE in AE reporting.

4.2.9 Pharmacokinetics and immunogenicity

4.2.9.1 Analysis of pharmacokinetics

All analyses of PK variables will be based on the PK analysis set as defined in Section 2.1.3.

Serum tezepelumab concentrations will be summarised at the protocol specified time points for the on-study-period using descriptive statistics (for the tezepelumab group only).

Serum samples for PK are scheduled to be collected at weeks 0, 12, EOT visit (or the premature IP discontinuation visit, where appropriate), and final follow-up at 12 weeks after EOT visit. Data will be assigned to weeks based on the windows defined in [Section 3.1.6](#).

The following criteria will also apply for data to be included in the summary table:

- Only pre-dose samples at week 0.
- Only pre-dose samples at trough time points (week 12) that was also between ≥ 21 and ≤ 35 days post the previous dose.
- Only samples at EOT visit/premature IP discontinuation visit that were taken between ≥ 21 and ≤ 35 days post the last dose.
- Only samples at final follow-up visit that were taken between ≥ 98 and ≤ 126 days post the last dose.

For descriptive statistics of tezepelumab concentrations:

- If, at a given time point, 50% or less of the concentrations are non-quantifiable (NQ), the geometric mean, coefficient of variation (CV), arithmetic mean and SD will be calculated by substituting the lower limit of quantification (LLOQ) divided by 2 for values which are NQ.
- If more than 50%, but not all, of the concentrations are NQ, the geometric mean, CV, arithmetic mean and SD will be reported as not calculable (NC)
- If all the concentrations are NQ, the geometric mean and arithmetic mean will be reported as NQ and the CV and SD as NC
- The median, minimum and maximum will also be reported.

The LLOQ of tezepelumab in serum will be 0.010 $\mu\text{g/mL}$.

The PK data may be merged with those from other clinical studies for a population-based meta-analysis. If performed, results of the meta-analysis will be presented in a separate pharmacometrics report outside of the CSR, and this is not considered further in this SAP.

4.2.9.2 Analysis of drug concentrations in BAL

BAL tezepelumab concentrations will be summarised at the protocol specified time points using descriptive statistics (for the tezepelumab group only)) separately from the CSR. For descriptive statistics of tezepelumab concentrations in BAL, the rules to handle non-

quantifiable concentrations will be the same as that for the serum tezepelumab PK data. The LLOQ of tezepelumab in BAL is TBD.

If appropriate, the tezepelumab concentrations in the epithelial lining fluid ($C_{teze,ELF}$) will be estimated based on the tezepelumab concentrations in BAL ($C_{teze,BAL}$) and the dilution factor (DF) derived based on the urea concentrations in serum ($C_{urea,serum}$) and BAL ($C_{urea,BAL}$) using the following equations:

$$DF = \frac{C_{urea,serum}}{C_{urea,BAL}}$$

$$C_{teze,ELF} = C_{teze,BAL} \times DF$$

If calculated, the ELF tezepelumab concentrations and ELF-to-serum tezepelumab concentrations ratio will be summarised at the protocol specified time points (week 0 and EOT visit) using descriptive statistics (for the tezepelumab group only). For descriptive statistics of tezepelumab concentrations in ELF and ELF-to-serum tezepelumab concentrations ratio, the rules to handle non-quantifiable concentrations will be the same as that for the serum tezepelumab PK data.

The results of this analysis will be reported separately from the CSR.

4.2.9.3 Analysis of immunogenicity

All analyses of immunogenicity variables will be based on the safety analysis set as defined in Section 2.1.3.

The number and percentages of ADA-positive subjects at each visit will be summarised by treatment group for the on-study period. Descriptive statistics including number of subjects, mean, SD, 1st quartile, median, 3rd quartile, and range of the actual ADA titres by treatment group and visit, where possible, will be provided.

The ADA status across the study for each subject will also be classified and summarised by treatment group. Specifically, the following ADA results will be evaluated as number and proportion of subjects in cohorts together with corresponding titre summaries. However, if the number of ADA positive subjects in the safety analysis set is small then the ADA variables may be listed only in the CSR:

- Subjects who are ADA positive at baseline and/or post-baseline (ADA prevalence).
- Subjects who are ADA positive at baseline only.
- Subjects who are ADA positive at baseline and positive in at least one post baseline measurement.
- Subjects who are ADA positive at baseline regardless of post-baseline result.
- Subjects who are ADA positive post-baseline.
- Subjects who are ADA positive post-baseline and ADA negative at baseline (treatment induced ADA positive).

- Subjects who are ADA persistently positive; persistently positive is defined as having at least 2 post-baseline ADA positive measurements (with ≥ 16 weeks between first and last positive) or an ADA positive result at the last available post-baseline assessment.
- Subjects who are ADA transiently positive; transiently positive is defined as having at least one post-baseline ADA positive measurement and not fulfilling the conditions for persistently positive.
- Subjects who are treatment boosted ADA positive, defined as baseline positive ADA titre that was boosted to a 4-fold or higher level following IP administration
- Subjects who are treatment emergent ADA (TE-ADA) positive (ADA incidence): defined as either treatment induced ADA positive or treatment boosted ADA positive.

For the overall ADA summary (i.e. calculation of the various ADA categories), all available ADA samples should be included in the analysis.

For ADA summaries at a single time point (e.g. baseline ADA or by visit) the corresponding titre summary will be based on the titre of the positive sample with the highest titre value for that particular visit.

For summaries across visits (e.g. ADA positive at any visit) the corresponding titre summaries will be based on the maximum titre of all positive samples for each subject.

The effect of ADA on PK and safety outcomes may be evaluated, if appropriate.

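### The across-visit ADA titre rule has no time restriction, so a pre-dose titre can be reported in the post-baseline, persistently positive and transiently positive rows

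*SAP*

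**What the plan says.** All of the relevant text on titres is in SAP section 4.2.9.3.

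- The ADA categories "will be evaluated as number and proportion of subjects in cohorts together with corresponding titre summaries".
- For the overall ADA summary, "all available ADA samples should be included in the analysis".
- For summaries across visits, "the corresponding titre summaries will be based on the maximum titre of all positive samples for each subject". The example given is a subject positive at any visit.
- For a single time point, the highest positive titre at that visit is used.

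Three of the listed categories are defined only by results after the first dose:

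- "Subjects who are ADA positive post-baseline", listed without regard to baseline status;
- persistently positive, where "persistently positive is defined as having at least 2 post-baseline ADA positive measurements" a stated time apart, or the last available post-baseline result is positive;
- transiently positive, where "transiently positive is defined as having at least one post-baseline ADA positive measurement and not fulfilling the conditions for persistently positive".

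A further category needs both times: "Subjects who are ADA positive at baseline and positive in at least one post baseline measurement".

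Section 3.4 has a serum ADA sample taken before the first administration. Section 3.1.1 defines the immunogenicity baseline as the last value before the first dose.

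**The concern.** The titre rule and the category definitions use different sets of samples. A category may look only at samples after dosing, while the titre attached to it is the maximum over every positive sample the subject has, including the pre-dose one. A baseline-positive subject can belong to any of the three post-baseline categories. If that subject's titre was highest before any drug was given, the row shows antibody that was already there.

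What is at stake is the meaning of the titre column in those rows. A reader takes it as the level reached after dosing. Section 3.4 has ADA assayed in all subjects regardless of arm, so the mislabelled value can arise in either group.

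**Working it through.** The SAP states no figure on this point, so there is none to reproduce. The check applies the written rule to titre patterns and sees which rows can take their maximum from the baseline sample.

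**One subject.** Assumed titres: baseline 160, then 40, 20 and negative at assumed weeks 12, 28 and 40.

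- The subject is positive post-baseline. Two positives lie 28 − 12 = 16 weeks apart, which meets the 16-week condition, so the subject is also persistently positive.
- Titre under the rule as written: max(160, 40, 20) = 160.
- Titre from post-baseline samples only: max(40, 20) = 40.
- Ratio: 160/40 = 4. This ratio follows entirely from the assumed titres.

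**All patterns on a grid.** Assume one baseline and three post-baseline samples, each negative, 10, 20, 40, 80 or 160. That gives 6⁴ = 1,296 patterns. Number the positive levels k = 1 to 5. For baseline level k, the post-baseline triples that are all below k and not all negative number k³ − 1. Summing gives 0 + 7 + 26 + 63 + 124 = 220.

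| Row | Patterns | Maximum is a baseline titre above every post-baseline titre |
|---|---|---|
| Positive post-baseline | 6 × 215 = 1,290 | 220 |
| Persistently positive | 1,290 − 60 = 1,230 | 220 − 20 = 200 |
| Transiently positive | 6 × 10 = 60 | 2 × (0+1+2+3+4) = 20 |
| Positive at both times | 5 × 215 = 1,075 | 220 |
| Treatment induced | 215 | 0 |
| Treatment boosted | 432 | 0 |
| Treatment emergent | 215 + 432 = 647 | 0 |

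The zeros follow from the definitions. Induced subjects are negative at baseline, and boosted subjects have a later titre at least four times the baseline one.

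**The reverse case.** In the row for subjects positive at baseline whatever follows, the overall maximum is a post-baseline titre in 208 + 189 + 152 + 91 + 0 = 640 of 5 × 216 = 1,080 patterns. In the baseline-only row the rule does no harm, because the baseline sample is the only positive one.

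These are counts of possible patterns, not expected frequencies. They show which rows are exposed, not how often.

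**The case against.** **The wording may already restrict the samples.** The example attached to the rule is positivity at any visit, which is the prevalence row, and there a maximum over all samples is right. Titre summaries that correspond to a category could be read as coming from the samples that define it. The instruction to include all available samples is tied to calculating the categories, not to choosing titres. This reading is possible. However, the sentence itself names the samples to use, and its example does not limit it to prevalence. A programmer following it would apply no filter.

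**The row positive at both times is not an error.** It is defined by both samples, so a baseline titre belongs there. This stands. That row only needs a statement of which titre is shown.

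**Baseline-defined rows may fall under the single-time-point rule.** They may, and the SAP should say so.

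**Three stronger inferences are not supported.**

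- A reader might infer that a falling titre is hidden. Section 4.2.9.3 separately requires titre statistics by treatment group and visit, so a fall would be visible there.
- A reader might infer that pre-existing antibody is reported as the response to treatment. The categories built to show that response (induced, boosted and treatment emergent) cannot be affected.
- A reader might infer that numbers will be small enough for one subject to dominate a row. The SAP does not say that few subjects will be ADA positive. It says only that if the number is small the variables may be listed, in which case the affected tables might not be produced.

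**Conclusion.** The point holds in a limited form. As written, the across-visit titre rule lets a pre-dose titre appear in three rows defined by post-baseline results only. It requires a subject who is positive at baseline, positive again later, and never later as high as before dosing.

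The consequence is descriptive. No count, percentage, test or endpoint changes, and the treatment-emergent rows and by-visit titres stand. The size cannot be derived from the SAP, because no rate of pre-existing ADA, titre distribution or trend after dosing is given. The 4-fold example and the pattern counts rest on an assumed titre grid and assumed sampling weeks. The conclusion itself rests only on the wording of section 4.2.9.3 and the existence of a pre-dose sample. This is a minor correction worth making.

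**What to change.** In section 4.2.9.3, qualify the across-visit rule by category:

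- positive post-baseline, persistently positive and transiently positive: maximum post-baseline titre;
- positive at baseline only, and positive at baseline whatever follows: baseline titre;
- ADA prevalence: maximum over all positive samples, as now;
- positive at both times: state which titre is shown, for example baseline and maximum post-baseline titres separately.

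The induced, boosted and treatment-emergent rows need no change, since their maximum is already a post-baseline titre. The cost is one sentence in the SAP and one filter in the ADA program. No category definition, analysis set or count is altered.

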5. INTERIM ANALYSES

No interim analyses are planned in this trial.

An independent Data and Safety Monitoring Board (DSMB) will safeguard the interests of subjects by assessing the safety of the intervention. The DSMB will review safety data on a regular basis as set out in a DSMB charter. The data for review will be outlined in a DSMB charter. The DSMB will have access to individual treatment codes and will be able to merge these with the collected study data whilst the study is ongoing.

The personnel involved in the clinical study at AstraZeneca will remain blinded to these analyses and will have no knowledge of the results presented to the DSMB.

6. CHANGE OF ANALYSIS FROM PROTOCOL

The analyses proposed using T2 status determined by RNA transcriptomics of bronchial brushings at baseline may now be performed using T2 status determined by three gene mean derived from RT-qPCR from LCM excised epithelium from FFPE biopsy tissue at baseline due to laboratory error resulting in data loss, reported as a serious breach. Analyses relating to the T2 status, ie, change from baseline to EOT in number of airway inflammatory cells per mm^2 across the spectrum of T2 status derived from RT-qPCR, will be exploratory endpoint in this study, pending technical feasibility, and will be reported separately from the CSR.

8. APPENDIX

8.1 Adverse events of special interest

8.1.1 Anaphylactic reactions

Potential anaphylactic reactions will be defined on the basis of Sampson's criteria (see [Sampson et al., 2006](#)). These will be identified using a modified Standardized MedDRA Query (SMQ), with additional constraints on the timing of the AE onset date relative to the timing of the injection.

Confirmed anaphylactic reactions will be those defined following medical review of the preferred terms identified as potential anaphylactic reactions, as well as any relevant supporting data.

Immune complex disease will be defined using the PT defining immune complex disease (depending on current MedDRA version).

AESIs and related definitions based on MedDRA terms are not included in this SAP to facilitate their maintenance (e.g. management of MedDRA version changes), and for convenience in using them directly in SAS programming. These detailed definitions will be finalised by the study team prior to unblinding of the trial, and provided together with the study datasets at the time of submission.

8.1.2 Malignancy

Malignancy will be defined on the basis of an SMQ.

AESIs and related definitions based on MedDRA terms are not included in this SAP to facilitate their maintenance (e.g. management of MedDRA version changes), and for convenience in using them directly in SAS programming. These detailed definitions will be finalised by the study team prior to unblinding of the trial, and provided together with the study datasets at the time of submission.

8.1.3 Helminth infections

Helminth infection will use an investigator-driven definition, i.e. will be directly determined from what is entered on the eCRF.

A subject will be considered to have this AESI if the subject has at least one preferred term where the dedicated Helminth Infection eCRF page was also completed for that event (linked by AE number), with AE onset date during the relevant study period for analysis.

8.1.4 Severe infections (as defined in the protocol)

Severe infections will use an investigator-driven definition, i.e. will be directly determined from what is entered on the eCRF.

A subject will be considered to have this AESI if the subject has at least one preferred term with AE onset date during the relevant study period for analysis, which satisfies the following:

- “AE Category” on Adverse Events eCRF page marked as “Severe Infection”, and one or more of the following:

- AE is serious (“Serious” on Adverse Events eCRF page marked as “Yes”), or
- AE required treatment with antiviral medications, intravenous antibiotics or medications for Helminth parasitic infection, or
- AE resulted in permanent discontinuation of study drug (“Action taken, investigational product” on Adverse Events eCRF page marked as “Drug permanently discontinued”).

8.1.5 Injection site reactions

Injection site reactions will use an investigator-driven definition, i.e. will be directly determined from what is entered on the eCRF.

A subject will be considered to have this AESI if the subject has at least one preferred term with AE onset date during the relevant study period for analysis, which has “AE category” on the Adverse Events eCRF page marked as “Injection Site Reaction”.

8.1.6 Opportunistic infections

Opportunistic infections will be defined using a pre-specified list of preferred terms (AZ defined SMQ).

AESIs and related definitions based on MedDRA terms are not included in this SAP to facilitate their maintenance (e.g. management of MedDRA version changes), and for convenience in using them directly in SAS programming. These detailed definitions will be finalised by the study team prior to unblinding of the trial, and provided together with the study datasets at the time of submission.

8.1.7 Guillain-Barre syndrome

Guillain-Barre syndrome will be defined using an SMQ.

AESIs and related definitions based on MedDRA terms are not included in this SAP to facilitate their maintenance (e.g. management of MedDRA version changes), and for convenience in using them directly in SAS programming. These detailed definitions will be finalised by the study team prior to unblinding of the trial, and provided together with the study datasets at the time of submission.

8.2 OCS conversion factors for prednisone equivalents

Total daily OCS dose will be converted to a prednisone equivalent using the following table:

Table 3 Estimated OCS dose therapy equivalence

Oral Corticosteroid	Approximate equivalence dose
Prednisone	10 mg
Prednisolone	10 mg
Cortisone	50 mg
Hydrocortisone	40 mg
Methylprednisolone	8 mg

Oral Corticosteroid	Approximate equivalence dose
Triamcinolone	8 mg
Betamethasone	1.2 mg
Dexamethasone	1.5 mg
Deflazacort	12 mg

For example, to convert a cortisone total daily dose to a prednisone equivalent total daily dose, a multiplication factor of $0.2 = 10/50$ should be used.

8.3 Additional reporting to assess the impact of the COVID-19 pandemic

In order to assess the impact of the COVID-19 pandemic on the planned analyses, further additional summaries and analyses will be conducted. These are described below, with the section of the main SAP in which they relate to. The start date of the COVID-19 pandemic is defined as 11th March 2020; the date the World Health Organisation (WHO) declared it a pandemic. Where applicable, as described below, data will be presented prior to the start of the pandemic, and during the pandemic. No post-pandemic period is defined as it is expected that the majority of subjects will have completed the study before the end date of the pandemic can be defined.

Section 2.2 Violations and Deviations

All COVID-19 related IPDs will be grouped as described in Section 2.2 and summarised together with all non-COVID-19 related IPDs as described in Section 4.2.1. A listing of all COVID-19 related protocol deviations (important and non-important PDs) will be provided.

An additional summary will be provided of IPDs related to COVID-19, and IPDs excluding COVID-19 related IPDs separately by treatment group for the FAS.

Section 4.2.1 Subject disposition, demography and baseline characteristics

The number of subjects randomised prior to the COVID-19 pandemic, and number of subjects ongoing in the study, as well as ongoing in the planned treatment period during the COVID-19 pandemic will be summarised by treatment group for the FAS. The total duration of follow-up for subjects during the study will be summarised, together with the duration of follow-up during the COVID-19 pandemic, for the FAS. The proportion of time on study during the pandemic will also be provided by treatment group.

The number and percentage of subjects with at least one missed scheduled visit or changed format of scheduled visit will be summarised by treatment group for the FAS. Changed format of scheduled visit will be grouped into “On-site, partial visit”, “Remote visit”, “Other”. The number of subjects discontinuing IP or withdrawing from the study due to COVID-19 will also be summarised by treatment group.

A listing of all subjects impacted by COVID-19 will be produced with details of changed or missed visits and change of location of IP administration or missed IP administration.

Section 4.2.3 Exposure and Compliance

The number of subjects with missed IP doses due to COVID-19, including consecutive missed doses, will be summarised by treatment group. In addition, the number of IP doses administered by location (home, other) will be summarised by treatment group, for the safety analysis set.

Section 4.2.4.1 Primary outcome variables - primary analysis

To investigate any difference in treatment effect due to any additional IP doses administered to subjects at unscheduled weeks 28, 32, 36, 40, 44 and 48 during the COVID-19 pandemic outbreak, additional sensitivity analysis will be performed including only subjects in the evaluable analysis set who had an EOT assessment at Week 28. Analyses of the primary endpoints of within subject change, expressed as a ratio, from baseline to Week 28 in airway submucosal inflammatory cells will be performed separately for eosinophils, neutrophils, T cells (CD3+, and CD4+), mast cells tryptase+ and mast cells chymase+, using the same ANCOVA model described for the primary variables in Section 4.2.1. Results will also be included in the forest plot for the primary. Descriptive statistics will also be presented.

Section 4.2.8.1 Adverse Events

The number and percentage of subjects reporting COVID-19 AEs (as defined based on the COVID-19 MedDRA terms) will be summarised by system organ class (SOC) and preferred term (PT) for the on-treatment and on-study periods.

In addition, if there are more than 10 subjects reporting COVID-19 AEs, then the AE listing will be repeated including only these subjects, with details of all AEs reported by these subjects

A listing of subjects tested for COVID-19 and including test result will be provided.

SIGNATURE PAGE

This is a representation of an electronic record that was signed electronically and this page is the manifestation of the electronic signature

Document Name: d5180c00013-sap-ed-3		
Document Title:	Statistical Analysis Plan Edition 3 15Nov2020	
Document ID:	Doc ID-003970585	
Version Label:	3.0 CURRENT LATEST APPROVED	
Server Date (dd-MMM-yyyy HH:mm 'UTC'Z)	Signed by	Meaning of Signature
18-Nov-2020 20:45 UTC	PPD [REDACTED]	Content Approval
18-Nov-2020 20:36 UTC	PPD [REDACTED]	Author Approval

Notes: (1) Document details as stored in ANGEL, an AstraZeneca document management system.

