1.2 Study design

[figure not shown]
This is a phase 2, multicentre, randomised, double-blind, placebo-controlled, parallel group study to evaluate the effect of tezepelumab on airway inflammation in approximately 110 adults with inadequately controlled moderate-to-severe asthma. Subjects will have background asthma therapy of medium- or high dose inhaled corticosteroids (ICS) plus at least one additional asthma controller medication, such as a long-acting β 2-agonist (LABA), leukotriene receptor antagonist (LTRA), long-acting muscarinic antagonist (LAMA), cromone, and theophylline, with or without maintenance oral corticosteroids (OCS) from screening and throughout the study including the follow-up period.

The study will consist of a screening/run-in period of up to 4 weeks, a treatment period of 28 weeks and a post-treatment follow-up period of 12 weeks. One dose level of tezepelumab, 210 mg will be compared with placebo administered subcutaneously every 4 weeks (Q4W) over the treatment period. Subjects who discontinue investigational product (IP) during the study will be encouraged to undergo appropriate study visits/procedures for the full 40-week period. Any new treatments that are initiated will be recorded. Subjects who complete the 28-week study visit will complete a 12 week off-treatment follow-up period for assessment of safety parameters and ADAs. During the COVID-19 pandemic, there is an option for patients to have an extra dose every 4 weeks up to 6 additional doses, as needed. For the last follow up visit, a phone call and/or a virtual visit can replace an on-site visit.

The study aims to randomise subjects across the spectrum of T2 status. To ensure this, the study will randomise approximately 30% of subjects with < 150 blood eosinophils/ μL , approximately 30% of subjects with $150 - < 300$ blood eosinophils/ μL and approximately 40% of subjects with ≥ 300 blood eosinophils/ μL .

For an overview of the study design see Figure 1.

Figure 1 Study Design

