2.1.1 Efficacy analysis set

Full analysis set (FAS)

This analysis set comprises all subjects randomised to study treatment who received at least one dose of IP, irrespective of their protocol adherence and continued participation in the study.

Evaluable analysis set

This analysis set comprises all subjects randomised to study treatment who completed at least 20 weeks of study treatment and had an EOT visit date not greater than 8 weeks after date of last dose of IP.

Efficacy analyses will be performed using all subjects in the evaluable analysis set unless otherwise stated, with subjects classified by their randomized treatment according to the intention-to-treat (ITT) principle. Subjects will be analysed according to their randomised treatment (including in the case of any discrepancies between randomised and actual treatment).

The evaluable analysis set and FAS specifies which subjects are included in efficacy analyses. Details of which data are included in efficacy analyses for these subjects are given in the respective sections, notably in Section 3.1.5 and Section 4.2.

Certain types of exploratory efficacy data are planned to be captured in a subset of participating subjects who have given an additional consent to participate in such a sub-study. Where this is the case, the analysis will use the subset of subjects in the evaluable analysis set for which any data of the relevant type are available. No formal sub-study analysis sets will be explicitly defined for this purpose.

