The following table summarises the visit windows to be used. “Visit window 1” corresponds to the full (mostly 4-weekly) protocol scheduling and will be used for all variables by default, including those variables which are not captured according to the full protocol schedule, and for which only certain weeks displayed in “Visit window 1” therefore apply. An assessment will be made during blinded review of the extent to which values for variables which do not follow the complete protocol schedule are falling outside the windows for the relevant weeks using “Visit window 1”. Following blinded review, a decision may be made to apply one of the alternative visit window rules displayed below to any such variables.

Table 1 Visit windows

Time point	Target day	Visit window 1	Visit window 2 (if needed)	Visit window 3 (if needed)	Visit window 4 (if needed)
Baseline (Week 0)	1	See Section 3.1.1 for baseline definitions			
Week 2	15				
Week 4	29	2-42			
Week 8	57	43-70			
Week 12	85	71-98	2-140		2-140
Week 16	113	99-126			
Week 20	141	127-154			
Week 24	169	155-182			
Week 28/EOT*	197/EOT*	183-210/EOT*	141-210/EOT*	2-210/EOT*	141-210/EOT*
Follow-up Week 32*	225				
Follow-up Week 36*	253				
Follow-up Week 40*	281	211-294	211-294		

* During the COVID-19 pandemic unscheduled visits may occur at week 28, 32, 36, 40, 44 or until 48 so that sites may perform EOT assessments 4 weeks after last dose of IP. After EOT visit, there will be post-treatment follow-up period of 12 weeks. Data from EOT visit will be summarised as “EOT” time point without visit window applied.

Finally, it should be noted that a visit window approach will not be used for data captured on a device daily by the subject, which will be aggregated for analysis at each relevant time point by using a weekly mean or similar approach. For this purpose, the definition of the weekly mean is provided in the relevant endpoint derivation sections of this SAP.

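### The COVID-19 sensitivity analysis asks about additional doses but selects on EOT week, so it also drops evaluable subjects who had no additional dose and a late EOT biopsy

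*SAP*

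**What the plan says.** Under its entry for Section 4.2.4.1, Appendix 8.3 states why the extra work is done: "To investigate any difference in treatment effect due to any additional IP doses administered to subjects at unscheduled weeks 28, 32, 36, 40, 44 and" (the list of weeks runs on to 48). The rule that follows is "additional sensitivity analysis will be performed including only subjects in the evaluable analysis set who had an EOT assessment at Week 28". It contains no condition on the number of doses received. The results go into the same forest plot as the primary analysis.

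Other parts of the SAP determine whom the rule catches:

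- Section 2.1.1 requires at least 20 weeks of study treatment for the evaluable set, and that the subject "had an EOT visit date not greater than 8 weeks after date of last dose of IP".
- Section 1.2 describes "a treatment period of 28 weeks and a post-treatment follow-up period of 12 weeks", with IP "administered subcutaneously every 4 weeks (Q4W) over the treatment period". It makes extra dosing optional during the pandemic: "there is an option for patients to have an extra dose every 4 weeks up to 6 additional doses, as needed".
- Section 3.1.6 assigns time points by assessment date and does not use nominal visit numbers. Table 1 gives Week 28 as days 183-210 in window 1. Alternative windows 2 to 4 start earlier, but all end at day 210. The footnote explains that unscheduled visits exist so that "sites may perform EOT assessments 4 weeks after last dose of IP". It adds that EOT data are summarised as one time point with no window.

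**The concern.** The question is about dosing and the filter is about the calendar. They select the same people only if every EOT after the Week 28 window was preceded by an additional dose. The SAP does not guarantee this: additional doses are optional, and the evaluable definition tolerates an EOT well beyond 4 weeks after the last dose.

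Where the two differ, the analysis removes two kinds of subject at once: those with additional doses, and those with none whose EOT biopsy was late. A change in the estimate cannot then be assigned to additional dosing, although that is the stated purpose and the natural reading of the forest plot. The analysis also gives up subjects who belong in a no-extra-dose comparison. No other sensitivity analysis specified for the primary endpoints separates the two: Section 4.2.6 leaves any others to be decided before database lock and points to Appendix 8.3.

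**Working it through.** **1. The plan's own figure, to fix the scale.** Section 1.3 states 80% power for eosinophils with 50 per arm, a 2-sided 10% test, a 2.7-fold effect and log-scale SDs of 1.87 and 2.06.

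- Effect: ln 2.7 = 0.993.
- Standard error: sqrt((1.87² + 2.06²)/50) = sqrt(7.7405/50) = 0.39.
- Power: 81.0% by the normal approximation and 80.6% by the noncentral t. The stated 80% is reproduced.
- Neutrophils (SDs 0.71 and 0.97): standard error sqrt((0.71² + 0.97²)/50) = 0.17; power above 99.9%, consistent with the stated figure of more than 90%.

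**2. Day arithmetic for a subject with no additional dose.** Day = 7 × week + 1. The last regular dose is not stated in the SAP. Dosing every 4 weeks, a 28-week treatment period and EOT 4 weeks after the last dose together imply Week 24.

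| Event | Day |
|---|---|
| Last regular dose, Week 24 | 7 × 24 + 1 = 169 |
| Planned EOT, 4 weeks later | 169 + 28 = 197 |
| Last day of the Week 28 window (all four windows) | 210 |
| Last evaluable EOT, 8 weeks after last dose | 169 + 56 = 225 |

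Days 211 to 225 (15 days, 42 to 56 days after the last dose) are therefore evaluable, need no additional dose and lie outside Week 28.

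**3. Can EOT week identify additional dosing?** One additional dose at Week 28 (day 197) with EOT 4 weeks later gives 197 + 28 = day 225. A subject with no additional dose and the latest permitted EOT also has day 225. EOT timing cannot tell these two apart; dose count can.

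**4. Is the retained set clean?** For an additional dose on day 197 to be followed by an EOT inside the window, the EOT would have to come within 210 − 197 = 13 days, against a planned 28. The retained set is essentially free of extra-dose subjects, so the fault lies in who is removed.

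**5. Size, under assumptions only.** The SAP gives neither the number of such subjects nor how much effect persists 6 to 8 weeks after a dose. Suppose a share f of evaluable subjects is late with no additional dose and retains a fraction a of the log effect, and that additional doses themselves change nothing. Then

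primary log ratio = −ln 2.7 × (1 − f + f × a); sensitivity log ratio = −ln 2.7; gap = ln 2.7 × f × (1 − a).

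| Assumption | Primary ratio | Sensitivity ratio | Log gap | Gap / SE, eosinophils | Gap / SE, neutrophils |
|---|---|---|---|---|---|
| f = 5%, a = 0.5 | 0.380 | 0.370 | 0.025 | 0.06 | 0.15 |
| f = 15%, a = 0 | 0.430 | 0.370 | 0.149 | 0.38 | 0.88 |

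The second row supposes that the whole effect has gone in every late subject, so it is an extreme. The 90% confidence interval for eosinophils spans a factor of exp(1.645 × 0.39) = 1.9 either way. Losing 5% to 15% of subjects widens an interval by sqrt(100/95) = 1.03 to sqrt(100/85) = 1.08.

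**The case against.** The best defence is that a Week 28 EOT is a reasonable proxy for no additional dose. The unscheduled visits were created so that a postponed biopsy could still follow a dose by 4 weeks, so a late EOT without an additional dose should be the exception. The rule also answers a coherent second question, since Appendix 8.3 analyses change from baseline to Week 28, the planned endpoint timing. Both points stand. They make the affected group probably small and justify keeping the Week 28 analysis. They do not make it an analysis of additional dosing, and the dosing record identifies that group directly.

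A further defence is that the appendix does not tie Week 28 to days 183-210, and the Table 1 footnote exempts EOT data from windowing. That is fair. Date-based assignment makes 183-210 the likelier reading, but the rule is under-specified. On a looser reading fewer late subjects would be dropped, yet the rule would still contain no dosing criterion.

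Some stronger inferences are tempting and are not supported:

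- *That early EOT visits are dropped too*, for example a last dose at Week 20 (day 141) with EOT on day 169. This needs window 1, because windows 2 to 4 all include day 169 and may be adopted after blinded review. It also needs a premature discontinuation visit to count as the EOT biopsy, which the SAP does not establish. Such a biopsy would be 169 − 141 = 28 days after the dose, hence on the dosing interval.
- *That extra-dose subjects contaminate the sensitivity set.* Step 4 of the working shows that they essentially do not.
- *That the analysis will produce a false extra-dose effect of a known size.* The shares and losses of effect in step 5 are assumptions with no source in the SAP, and the resulting gaps are small against the eosinophil interval.
- *That the primary result is biased.* The selection rule touches only the appendix analysis.

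**Conclusion.** The mismatch is real and limited. An evaluable subject with no additional dose and an EOT on days 211 to 225 is removed together with the extra-dose subjects, so a difference from the primary estimate mixes additional dosing with late biopsy timing. This rests on the last regular dose being at Week 24 (inferred) and on Week 28 carrying a Table 1 window.

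How many subjects are affected cannot be determined from the SAP, and the size of any shift is unknown. Under the assumed range it is 0.06 to 0.38 standard errors for eosinophils. For neutrophils, which are more precisely estimated, it could reach 0.88, but only at the extreme assumption. The trial reports nominal p-values and this is one appendix analysis. The reason to change it is that the row would not answer its own question and a row that does is readily available.

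**What to change.** In Appendix 8.3, define the sensitivity set as evaluable subjects who received no additional IP dose (none at unscheduled weeks 28 to 48), whatever their EOT day. Keep the Week 28 restriction as a separate row, with days 183-210 written into the rule, and label it as a timing analysis.

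The cost is a sentence or two of text, one flag derived from existing dosing data, and one more row in the forest plot. The last is the only real downside.

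As an editorial matter, the same entry refers to Section 4.2.1 for the ANCOVA model. That section covers disposition and baseline characteristics; the model is in Section 4.2.4.1, and the reference should be corrected.
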